#### 7.4.2. Summary Measure

- Mean treatment difference on change from baseline in clinic trough FEV1 over the first 24 weeks of the treatment period (weighted mean)
- Mean treatment difference on change from baseline in home daily trough FEV1 over the first 24 weeks of the treatment period
- Mean treatment difference on change from baseline in home daily PM FEV1 over the first 24 weeks of the treatment period
- Rate ratio on annualized rate of severe asthma exacerbations
- Hazard Ratio on time to first severe asthma exacerbation
- Hazard Ratio on time to first moderate/severe asthma exacerbation
- Odds ratio on percent of patients meeting a responder threshold of  $\geq 0.5$  points improvement (decrease) from baseline for the ACQ-7 at Week 24
- Odds ratio on percent of patients meeting a responder threshold of  $\geq 0.5$  points improvement (decrease) from baseline for the ACQ-6 at Week 24
- Odds ratio on percentage of patients meeting a responder threshold of  $\geq 0.5$  points improvement (decrease) from baseline for the ACQ-5 at Week 24
- Odds ratio on percentage of patients that have achieved asthma control based on ACQ-7 (i.e. a total score  $\leq 0.75$ ) at both Week 12 and Week 24
- Odds ratio on percentage of patients that have achieved asthma control based on ACQ-6 (i.e. a total score  $\leq 0.75$ ) at both Week 12 and Week 24
- Odds ratio on percentage of patients that have achieved asthma control based on ACQ-5 (i.e. a total score  $\leq 0.75$ ) at both Week 12 and Week 24
- Mean treatment difference on change from baseline in SGRQ domain scores (symptoms, activity, impact) at Week 24
- Odds ratio on percent of patients meeting a responder threshold of  $\geq 4$  points improvement (decrease) from baseline for the SGRQ total score at Week 24
- Mean treatment difference on change from baseline in E-RS domain scores (breathlessness, cough and sputum, chest) over Weeks 21-24 (inclusive) of the treatment period
- Odds ratio on percent of patients meeting a responder threshold of  $\geq 2$  points improvement (decrease) from baseline for the E-RS total score over Weeks 21-24 (inclusive) of the treatment period
- Mean treatment difference on change from baseline in the Asthma Quality of Life Questionnaire (AQLQ) total score at Week 24
- Odds ratio on percent of patients meeting a responder threshold of  $\geq 0.5$  points improvement (increase) from baseline for the AQLQ total score at Week 24
- Mean treatment difference on change from baseline in morning (AM) pre-dose Peak Expiratory Flow (PEF) over the first 24 weeks of the treatment period

- Mean treatment difference on change from baseline in evening (PM) PEF over the first 24 weeks of the treatment period
- Mean treatment difference on change from baseline in the percentage of symptom-free days over the first 24 weeks of the treatment period
- Mean treatment difference on change from baseline in the percentage of rescue medication-free days over the first 24 weeks of the treatment period
- Mean treatment difference on change from baseline in daily rescue medication use over the first 24 weeks of the treatment period.
- Unscheduled asthma-related healthcare resource utilization over the first 24 weeks of the treatment period.

**7.4.3. Population of Interest**

The Other efficacy analyses will be based on the Intent-To-Treat population

**7.4.4. Strategy for Intercurrent (Post-Randomization) Events**

No imputation will be made for missing data.

In general, a “treatment policy” strategy will be used to handle all intercurrent events, as described in Section 7.1.4, with the exception of the analyses of responders and asthma control.

For these analyses, a “treatment policy” strategy will be used to handle the intercurrent event of early discontinuation from study treatment, and a “composite” strategy will be used to handle the intercurrent event of premature withdrawal from study, where subjects who withdraw from the study prior to the timepoint of interest are considered non-responders at that timepoint. Participants with missing data at the timepoint of interest, regardless of treatment status, will be considered as non-responders. The endpoint analyzed will therefore essentially be the percent of participants who do not prematurely discontinue from the study, have data available at the timepoint and meet the responder threshold.

**7.4.4.1. Statistical Methodology Specification**

Endpoint
Mean change from baseline in clinic trough FEV 1 over the first 24 weeks of the treatment period
Model Specification

 
• Clinic trough FEV1 over the first 24 weeks of the treatment period and the change from baseline will be summarized.
 
• Baseline value is defined in Section 5.2.
 
• The analysis is based the on- and post-treatment (de facto) type estimand, including all clinic trough FEV1 data collected at all scheduled clinic visits prior to and on Week 24 (both on- and
 

post-treatment). The derivation of clinic trough FEV1 AUC0-24w will use all data collected at Baseline, Weeks 4, 12, and 24.

- Change from baseline in clinic trough FEV1 over the first 24 Weeks will be analyzed using an ANCOVA model.
- Terms in the model:
  - Covariates:
    - Categorical: treatment group, sex, region, pre-study ICS dosage at screening,
    - Continuous: age, baseline value for clinic FEV1
- The LS mean FEV1 over the first 24 weeks and LS mean change from baseline over the first 24 weeks will be estimated using the observed marginal distributions of the study population covariates by inclusion of the OM (observed margins) option in SAS.

#### Model Checking & Diagnostics

- Refer to [Appendix 8: Model Checking and Diagnostics for Statistical Analyses](#).

#### Model Results Presentation

- Summary statistics of the absolute and change from baseline in FEV1 over the first 24 weeks will be presented.
- Least-Squares (LS) means and LS mean change from baseline values for each treatment group will be presented with their associated standard errors. The estimated treatment difference along with corresponding standard error, 95% CI and unadjusted p-value will be presented for all treatment comparisons specified in Section 7.
- The LS mean change from baseline and LS mean treatment differences (and associated 95% CIs) for the comparisons of the two FF/UMEC/VI vs. a FF/VI at a given FF dose will also be presented graphically at Week 24, for each of the FF doses in two separate panels.

#### Endpoints

- Mean change from baseline in home daily trough FEV1 over the first 24 weeks of the treatment period
- Mean change from baseline in home daily PM FEV1 over the first 24 weeks of the treatment period
- Mean change from baseline in home daily morning (AM) pre-dose PEF over the first 24 weeks of the treatment period
- Mean change from baseline in home daily evening (PM) PEF over the first 24 weeks of the treatment period
- Mean change from baseline in E-RS Breathlessness scores over Weeks 21-24 (inclusive) of the treatment period
- Mean change from baseline in E-RS Cough & Sputum scores over Weeks 21-24 (inclusive) of the treatment period
- Mean change from baseline in E-RS Chest Symptoms scores over Weeks 21-24 (inclusive) of the treatment period
- Mean change from baseline in the percentage of symptom-free days over the first 24 weeks of the treatment period
- Mean change from baseline in the percentage of rescue medication-free days over the first 24 weeks of the treatment period
- Mean change from baseline in daily rescue medication use over the first 24 weeks of the

treatment period.
Model Specification

 
• These analyses will be performed using an MMRM model as for the E-RS data detailed in Section 7.3.5.1, using the on- and post-treatment (de facto) type estimand.
 
• The home daily trough FEV1, PM FEV1, AM PEF and PM PEF endpoints will be analyzed and presented using unpooled doses.
 
• The E-RS domains, percentage of symptom free days, percentage of rescue medication free days and daily rescue medication use will be analyzed and presented using the pooled FF doses.
 
• The home daily trough FEV1, PM FEV1, AM PEF and PM PEF endpoints will also be summarized in 1 weekly periods up to week 52.
 
• To assess for time to maximal effect of UMEC when comparing FF/UMEC/VI to FF/VI, weekly changes from baseline in Home Daily Trough FEV1 over the first 8 weeks of the treatment period will also be analyzed using the same MMRM detailed in Section 7.3.5.1. Here the period term is:             
 
○ Week 1, Week 2, Week 3, Week 4, Week 5, Week 6, Week 7, Week 8
 
 
 
• The LS mean change from baseline and LS mean treatment difference in percentage of symptom-free days and percentage of rescue medication-free days will also be presented as the equivalent number of additional symptom-free/rescue medication-free days per week.
 

Model Checking & Diagnostics

 
• Refer to Appendix 8: Model Checking and Diagnostics for Statistical Analyses
 

Model Results Presentation

 
• These analyses will be presented as for the E-RS data detailed in Section 7.3.5.1. Box plots and empirical distribution plots will not be presented.
 
• A plot of the LS mean change and LS mean treatment difference will be produced for the Home Daily Trough FEV1 data for the 1-weekly intervals up to week 8 (in a similar manner to the 4-weekly data up to week 24).
 
• A line plot of the unadjusted weekly mean change from baseline in home daily trough FEV1, PM FEV1, AM and PM PEF will be presented up to 24 weeks.
 
• For the E-RS domain (Breathlessness, cough & sputum and chest symptom) scores, these will be included in the same summaries and presented by domain. A forest plot will display the treatment estimate and 95% CI for the E-RS total score and domain scores at Weeks 21- 24.
 

Endpoint

 
• Annualized rate of severe asthma exacerbations
 

Model Specification

 
• Data for weeks 1-52 will be analyzed using a generalized mixed model as specified in Section 7.2.6 based on the on- and post-treatment (de facto) type estimand, presenting both unpooled and pooled FF dose treatment comparisons.
 

Model Checking & Diagnostics

 
• Refer to Appendix 8: Model Checking and Diagnostics for Statistical Analyses
 

Model Results Presentation

 
• See Section 7.2.6
 

Endpoints

 
• Time to first severe asthma exacerbation
 
• Time to first moderate/severe asthma exacerbation
 

Model Specification

 
• Cox's proportional hazards model
 
• All asthma exacerbations observed during the study (on- or post-treatment) will be used in the analyses
 
• Terms in the model: 
 
• Response: time to first severe (or moderate/severe) asthma exacerbation during the study (both on- and post-treatment)
 
• Covariates: 
 
○ Categorical: treatment group, sex, region, pre-study ICS dosage at screening, severe asthma exacerbations in the previous year (0, 1, >=2).
 
○ Continuous: age
 
 
 
 
 
• The 'exact' method will be used for handling ties. If the analysis will not run using the 'exact' method, then the 'Efron' method for handling ties will be used instead.
 
• For the pooled analysis: 
 
• All 6-arm data are included in the model.
 
• LSMESTIMATE statement will be used with the treatment code as specified Section 7.
 
• The analyses will be repeated using unpooled data.
 
 
 

Model Checking & Diagnostics

 
• Refer to Appendix 8: Model Checking and Diagnostics for Statistical Analyses
 

Model Results Presentation

 
• Hazard ratios for pairwise treatment comparisons with associated 95% CIs and p-values will be presented.
 
• Kaplan-Meier survivor functions will be obtained for each treatment group using PROC LIFETEST with a TIME statement.
 

Endpoints

 
• Percent of patients meeting a responder threshold of <math>\geq 0.5</math> points improvement (decrease) from baseline for the ACQ-7 at Week 24
 
• Percent of patients meeting a responder threshold of <math>\geq 0.5</math> points improvement (decrease) from baseline for the ACQ-6 at Week 24
 
• Percentage of patients meeting a responder threshold of <math>\geq 0.5</math> points improvement (decrease) from baseline for the ACQ-5 at Week 24
 
• Percent of patients meeting a responder threshold of <math>\geq 4</math> points improvement (decrease) from baseline for the SGRQ total score at Week 24
 
• Percent of patients meeting a responder threshold of <math>\geq 2</math> points improvement (decrease) from baseline for the E-RS total score over Weeks 21-24 (inclusive) of the treatment period
 
• Percent of patients meeting a responder threshold of <math>\geq 0.5</math> points improvement (increase) from baseline for the AQLQ total score at Week 24
 

Model Specification

 
• The analysis includes on-and post-treatment data and is based on the ITT population.
 

- For details of handling missing data, see Section [11.7.2](#).
- Analyses for the ACQ-7, SGRQ and E-RS total score will present unpooled and pooled FF doses treatment comparisons.
- Analyses for the ACQ-5, ACQ-6 and AQLQ will be carried out for the pooled FF doses.
- Percent of participants meeting the responder threshold will be summarized by period, and analyzed using a generalized linear model (logistic regression), including all data up to week 24.
- Computation of confidence intervals for the odds ratios is based on the individual Wald tests calculated on the log scale and then back transformed.
- Period:
  - ACQ-5, ACQ-6, ACQ-7, AQLQ: Clinic visits at Week 4, 12 and 24
  - SGRQ: Clinic visits Week 12 and 24
  - E-RS: Weeks 1-4, Weeks 5-8, Weeks 9-12, Weeks 13-16, Weeks 17-20, Weeks 21-24.
- Terms in the model:
  - Dependent Variable: Responder (Yes/No)
  - Covariates:
    - Categorical: treatment group, sex, region, pre-study ICS dosage at screening and period.
    - Continuous: age, Baseline value
    - Interaction: Baseline\*period, treatment\*period
- Link function: Logit
- All 6-arm data are included in the model.
- Where the output presents the pooled FF doses, LSMESTIMATE statement will be used with the treatment code as specified Section [7](#).
- The model will be fitted with an unstructured variance-covariance matrix.
- The OM option in SAS will be used.

#### Model Checking & Diagnostics

- Refer to [Appendix 8: Model Checking and Diagnostics for Statistical Analyses](#)

#### Model Results Presentation

- Number and percentage of responders and non-responders for each treatment at each Week will be presented. The number of non-responders due to missing data will also be presented.
- The odds ratio for all treatment comparisons as specified in Section [7](#), with associated 95% CI and p-value will be presented by visit.
- A forest plot displaying the odds ratios (and 95% CI) for the primary treatment comparisons as specified in Section [7](#) at week 24 (weeks 21-24 for the E-RS endpoint) will be presented.

#### Endpoints

- Percentage of patients that have achieved asthma control based on ACQ-7 (i.e. a total score  $\leq 0.75$ ) at both Week 12 and Week 24
- Percentage of patients that have achieved asthma control based on ACQ-6 (i.e. a total score  $\leq 0.75$ ) at both Week 12 and Week 24
- Percentage of patients that have achieved asthma control based on ACQ-5 (i.e. a total score  $\leq 0.75$ ) at both Week 12 and Week 24

#### Model Specification

- The analysis includes on-and post-treatment data and is based on the ITT population.
- For details of handling missing data, see Section [11.7.2](#).
- Analysis for the ACQ-7 will present unpooled and pooled FF dose treatment comparisons.

 
• Analyses for the ACQ-5 and ACQ-6 will be carried out for the pooled FF doses.
 
• Percent of participants meeting the asthma control criterion will be summarized and analyzed using a generalized linear model (logistic regression).
 
• Computation of confidence intervals for the odds ratios is based on the individual Wald tests calculated on the log scale and then back transformed.
   
• Terms in the model:             
 
○ Dependent Variable: Asthma control (Yes/No)
 
○ Covariates:                 
 
▪ Categorical: treatment group, sex, region and pre-study ICS dosage at screening
 
▪ Continuous: age, Baseline value
 
 
 
 
 
• Link function: Logit
 
• All 6-arm data are included in the model.
 
• Where the output presents the pooled FF doses, LSMESTIMATE statement will be used with the treatment code as specified Section 7.
 
• The model will be fitted with an unstructured variance-covariance matrix.
 
• The OM option in SAS will be used.
 

Model Checking & Diagnostics

 
• Refer to Appendix 8: Model Checking and Diagnostics for Statistical Analyses
 

Model Results Presentation

 
• Number and percentage of participants with and without asthma control for each treatment. The number of participants without asthma control due to missing data will also be presented.
 
• Odds ratio for treatment comparison with associated 95% CI and p-value as specified Section 7.
 
• A forest plot displaying the odds ratios (and 95% CI) for the primary treatment comparisons as specified in Section 7 at week 24 will be presented.
 

Endpoint

 
• Mean change from baseline in SGRQ domain scores at Week 24
 

Model Specification

 
• Change from baseline in SGRQ domain scores will be summarized and analyzed as for the SGRQ total score as specified in Section 7.3.5.1, for each domain separately.
 
• Summaries and analyses will use the on- and post-treatment (de facto) type estimand and be presented for pooled FF doses.
 

Model Checking & Diagnostics

 
• Refer to Appendix 8: Model Checking and Diagnostics for Statistical Analyses
 

Model Results Presentation

 
• As for the SGRQ specified in Section 7.3.5.1. Summaries and analyses will be presented by domain. A forest plot will display the treatment estimate and 95% CI for the SGRQ total score and domain scores at Week 24.
 

Endpoint

 
• Mean change from baseline in AQLQ total score at Week 24
 

Model Specification

 
• Change from baseline in AQLQ total score will be summarized and analyzed as for the SGRQ endpoint as specified in Section 7.3.5.1.
 
• Summaries and analyses will use the on- and post-treatment (de facto) type estimand and be presented for pooled FF.
 

Model Checking & Diagnostics

 
• Refer to Appendix 8: Model Checking and Diagnostics for Statistical Analyses
 

Model Results Presentation

 
• As for the SGRQ specified in Section 7.3.5.1.
 

Other Statistical Analyses
Endpoints

 
• Unscheduled asthma-related healthcare resource utilization over the first 24 weeks.
 
• WPAI-SHP
 
• Global assessment of severity
 
• Global assessment of response to treatment
 

Model Specification

 
• Summaries will use the on- and post-treatment (de facto) type estimand and be presented for unpooled data.
 
• No formal statistical analyses will be carried out.
 
• Unscheduled asthma-related healthcare resource utilization will also be summarized by contact type (related to an exacerbation/not related to an exacerbation) and up to 52 weeks for subjects with <math>\geq 36</math> Weeks of planned treatment exposure.
 

Model Checking & Diagnostics
Not applicable
Model Results Presentation

 
• Summary statistics appropriate for the data collected at visits where data was collected.
 

## 8. SAFETY ANALYSES

All safety analyses will be based on the ITT population. On-treatment safety data collected at scheduled clinic visits will be summarized and analyzed by treatment and by visit, unless otherwise specified. On-treatment adverse events and post-treatment adverse events will be summarized separately. All data will be listed, unless otherwise specified.

An overview of the planned analyses is provided below. The full details of safety analysis data displays are presented in [Appendix 10: List of Data Displays](#)

	Absolute			Change from Baseline		
	Summary		Individual	Summary		Individual
	T	F	L	T	F	L
Exposure						
Extent of Treatment Exposure (unpooled and pooled FF doses)	Y					
Post-Treatment Duration on Study	Y					
Adverse Events (AEs)						
Relationship of AE System Organ Class, Preferred Term and Verbatim Text			Y 			
AEs during screening/ run-in period	Y		Y 			
AEs during stabilization period	Y		Y 			
Overview of On-Treatment AEs	Y					
On-Treatment AEs	Y		Y			
On-Treatment AEs adjusted for exposure (per thousand person-years)	Y					
On-Treatment AEs in the respiratory, thoracic and mediastinal disorders SOC	Y					
On-Treatment AEs in the respiratory, thoracic and mediastinal disorders SOC (per thousand person-years)	Y					
Post-Treatment AEs during the study	Y		Y			
Post-Study AEs	Y		Y			
On Treatment AEs during Weeks 1-24	Y					
On Treatment AEs during Weeks 1-36 for participants with ≥ 36 weeks of planned treatment exposure	Y					
On Treatment AEs during Weeks 1-52 for participants with 52 weeks of planned treatment	Y					

	Absolute			Change from Baseline		
	Summary		Individual	Summary		Individual
	T	F	L	T	F	L
exposure						
On-Treatment Drug-Related AEs	Y					
On-Treatment Drug-Related AEs during the study adjusted for exposure (per thousand person-years)	Y					
Post-Treatment Drug-Related AEs	Y					
On-Treatment SAEs	Y					
On-Treatment SAEs adjusted for exposure (per thousand person-years)	Y					
Post-Treatment SAEs	Y					
Non-fatal SAEs			Y			
Fatal SAEs			Y			
On-Treatment Drug-Related SAEs	Y					
On-Treatment Drug-Related SAEs adjusted for exposure (per thousand person-years)	Y					
On-Treatment SAEs during Weeks 1-24	Y					
On-Treatment SAEs during Weeks 1-36 for participants with $\geq$ 36 weeks of planned treatment exposure	Y					
On-Treatment SAEs during Weeks 1-52 for participants with 52 weeks of planned treatment exposure	Y					
On-Treatment AEs Leading to Permanent Discontinuation of Study Drug or Withdrawal from Study	Y		Y			
Post-Treatment AEs Leading to Withdrawal from Study	Y		Y			
On-Treatment AESIs	Y		Y			
On-Treatment AESIs adjusted for exposure (per thousand person-years)	Y					
Post-treatment AESIs	Y					
On-Treatment AESIs during Weeks 1-24	Y					
On-Treatment AESIs during Weeks 1-36 for participants with $\geq$ 36 weeks of planned treatment exposure	Y					
On-Treatment AESIs during Weeks 1-52 for participants with 52 weeks of planned treatment	Y					

	Absolute			Change from Baseline		
	Summary		Individual	Summary		Individual
	T	F	L	T	F	L
exposure						
On-Treatment SAEs of Special Interest	Y		Y			
On-Treatment SAEs of Special Interest adjusted for exposure (per thousand person-years)	Y					
Post-treatment SAEs of special interest	Y					
On-treatment AEs (3% or More of Participants in Any Treatment Group)	Y					
The 10 Most Frequent On-treatment Adverse Events in Each Treatment Group	Y					
On-Treatment AEs during Study by Subgroups	Y					
Subject Numbers for Individual AEs			Y			
Subject Numbers for On-Treatment AEs of Special Interest			Y			
MACE						
On-Treatment Major Adverse Cardiac Events (Narrow Definition)	Y					
On-Treatment Major Adverse Cardiac Events (Broad Definition)	Y					
On-Treatment Major Adverse Cardiac Events (Narrow Definition) adjusted for exposure (per thousand person-years)	Y					
On-Treatment Major Adverse Cardiac Events (Broad Definition) adjusted for exposure (per thousand person-years)	Y					
Pneumonia and radiography (Chest X-rays)						
On-Treatment Pneumonia and radiography (Chest X-rays)	Y		Y			
Liver Events						
Medical conditions for participants with liver stopping events			Y			
Liver Event Results and Time of Event Relative to Treatment			Y			
Liver Event Substance Use			Y			
Liver Event Information for RUCAM Score			Y			
Liver Biopsy Details			Y			
Liver Imaging Details			Y			

	Absolute			Change from Baseline		
	Summary		Individual	Summary		Individual
	T	F	L	T	F	L
Laboratory Parameters						
Chemistry Values for Participants with at Least One Value Outside the Normal Range			Y			
Chemistry Data	Y	Y		Y	Y	
Chemistry Data Outside the Normal Range	Y					
Chemistry Changes from Baseline Relative to the Normal Range	Y					
Hematology Values for Participants with at Least One Value Outside the Normal Range			Y			
Hematology Data	Y	Y		Y	Y	
Hematology Data Outside the Normal Range	Y					
Hematology Changes from Baseline Relative to the Normal Range	Y					
Worst Case Urinalysis Results Post-Baseline Relative to Baseline				Y		Y
Vital Signs						
Vital Sign Data (Pulse Rate, Sys BP, Dia BP) 	Y		Y	Y	Y 	
12-Lead ECGs						
ECG Values 	Y			Y	Y 	Y
ECG Findings	Y		Y			
ECG Findings Shifts from Baseline	Y					
QTcF Categories	Y			Y		
ECG Abnormalities	Y		Y			Y
Maximum Post-Baseline QTcF	Y	Y		Y	Y	

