9.3. Data Analysis Considerations

9.3.1. Analysis Populations

The following subject populations will be identified:

All Subjects Enrolled Population: This population will comprise all subjects for whom a record exists on the study database, including pre-screened subjects that sign the informed consent document but do not complete a Visit 1 (screening) procedure (i.e., pre-screening failures), or subjects that complete at least one Visit 1 procedure but do not enter the run-in period (i.e., screening failures). This population will be used for the summary of subject disposition.

All Subjects Screened Population: This population contains all subjects that complete at least one Visit 1 (Screening) procedure. This population will be used for the summary of subject disposition (including reasons for screening failures, run-in failures, and stabilization failures) and for the listing of AEs and SAEs for non-randomized subjects.

Intent-to-Treat (ITT) Population: This population will comprise all randomized subjects, excluding those who were randomized in error. A subject who is recorded as a screen failure, run-in failure, or stabilization failure, but is randomized and does not receive a dose of study treatment, is considered to be randomized in error. Any other subject who receives a randomization number will be considered to have been randomized. This will constitute the primary population for all efficacy and safety analyses.

Pharmacokinetic (PK) population: This population will comprise all subjects in the ITT Population for whom a PK sample was obtained and analyzed.

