### 11.5.2. Reporting Standards

Reporting Standards	
General	

 
Displays will use the term “Subjects” to refer to “Participants”.
 
The current GSK Pooled Data Standards Library (IDSL) will be applied for reporting, unless otherwise stated: 
 
4.03 to 4.23: General Principles
 
5.01 to 5.08: Principles Related to Data Listings
 
6.01 to 6.11: Principles Related to Summary Tables
 
7.01 to 7.13: Principles Related to Graphics
 
 
 
	
Formats	

 
All data (including data collected following study treatment discontinuation [post-treatment]) will be reported according to the treatment to which the participant was randomized unless otherwise stated. However, there may be additional adhoc displays for individual participants using the actual treatment received.
 
The reported precision of data will follow IDSL statistical principles but may be adjusted to a clinically interpretable number of decimal places.
 
In most cases, percentages between 1% and 99%, inclusive, will be rounded to integers. Percentages greater than 0%, but less than 1%, will be reported as <1%, and percentages greater than 99%, but less than 100%, will be reported as >99%. For some rare events, percentages may be reported in 1 decimal point. In this case, percentages greater than 0%,
 
	

Reporting Standards	

but less than 0.1%, will be reported as <0.1%.
 
 
Numeric data will be reported at the precision collected on the eCRF.
 
The reported precision from non eCRF sources will follow the IDSL statistical principles but may be adjusted to a clinically interpretable number of decimal places.
 
	
Planned and Actual Time	

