**Planned and Actual Randomized Treatment**

For participants who received the correct treatment throughout the study, the actual treatment will be the same as the planned treatment. For participants who received an incorrect treatment, the actual treatment will be derived as follows:

- If the number of doses on an incorrect treatment is less than the number of doses on the planned treatment, then the actual treatment is assigned as planned treatment.
- If the number of doses on an incorrect treatment is greater than the number of doses on the planned treatment, then the actual treatment is assigned as the incorrect treatment.
- If the number of doses on an incorrect treatment and planned treatment are the same, the actual treatment is assigned as the treatment with the highest UMEC and/or FF dose.
- If an incorrect container was dispensed and not returned, such that it is not possible to ascertain whether or not any doses were taken from the incorrect container, it will be assumed that the participant took all possible doses from this container (i.e., 30 doses in total).

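### Safety tables are by randomized arm in the ITT population, so participants who mainly took another treatment, or took none, are counted under a dose they did not mainly take; the effect is probably small and matters only for rare events.

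*SAP*

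**What the plan says.** SAP Section 8 fixes the population: "All safety analyses will be based on the ITT population". Protocol Section 9.3.1 says the same of the ITT set: "This will constitute the primary population for all efficacy and safety analyses". The arm is set in SAP Section 11.5.2 (Formats), under which all data, including data collected after treatment discontinuation, "will be reported according to the treatment to which the participant was randomized unless otherwise stated". Section 8 states nothing different, and Tables 3.1 to 3.90 in Section 11.10.8 are all labelled ITT. For treatment actually received, Section 11.5.2 offers only that "there may be additional adhoc displays for individual participants using the actual treatment received".

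SAP Section 11.6.1 nevertheless derives actual treatment by majority of doses:

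- Wrong doses in the minority: the participant keeps the planned treatment.
- Wrong doses in the majority: the participant is reclassified to the wrong treatment.
- A tie: "the actual treatment is assigned as the treatment with the highest UMEC and/or FF dose".
- A wrong container that is not returned, so that its use cannot be established: the participant is taken to have used every dose in it, 30 in all.

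The result feeds Listing 4 and the Pop PK dataset (SAP Section 9.1, Table 1). It feeds no safety table.

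On undosed participants, the ITT definition (Protocol 9.3.1; SAP Sections 4 and 11.6.1) removes a randomized, undosed participant only if that person is also recorded as a screen, run-in or stabilization failure. SAP Sections 5.2 and 11.4 provide for others. They give a baseline rule for participants who received no randomized treatment and class all their post-baseline data before the final visit as post-treatment.

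**The concern.** A safety table should describe people by what they were exposed to. Misallocation here can cross UMEC 0, 31.25 and 62.5 mcg, or the two FF doses. If it is unrelated to outcome, mixing exposure between arms would be expected to pull dose-related differences toward zero, which is the non-conservative direction for safety.

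Dose attribution carries weight in this trial. Protocol Section 4.5 notes that UMEC 31.25 mcg was not assessed in the earlier dose-ranging study and that its safety profile will be assessed here. Protocol Section 4.6.1 reports pneumonia in earlier FF/VI asthma studies at 8.5 per 1000 patient-years on 100/25 and 18.3 on 200/25, with wide, overlapping intervals.

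The SAP also prefers actual over assigned status elsewhere: Section 2.1 replaces the randomized ICS stratum with the actual one. Undosed participants raise a separate question, because they add to a percentage denominator with no chance of an on-treatment event.

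**Working it through.** The plan states no figure for this point, so there is none to reproduce. The check applies the SAP's own majority rule.

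**Inputs.** 30 doses per container (SAP 11.6.1; Protocol 6.1, Table 3). Once-daily dosing, with last visits at Day 169, 253 or 365 (Protocol 7.1), so N = 169, 253 or 365 doses if none is missed.

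**Step 1: when actual differs from randomized treatment.** Wrong doses W must exceed N − W, so W > N/2.

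| Last visit | N | Wrong doses needed | Fully used wrong containers | One fewer container | One container's share |
|---|---|---|---|---|---|
| Week 24 | 169 | 85 | 3 (90 against 79) | 60 against 109 | 30/169 = 17.8% |
| Week 36 | 253 | 127 | 5 (150 against 103) | 120 against 133 | 30/253 = 11.9% |
| Week 52 | 365 | 183 | 7 (210 against 155) | 180 against 185 | 30/365 = 8.2% |

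For a single container, 30 > T − 30 requires total doses T ≤ 59. T = 60 is a tie, which reassigns the participant only if the wrong treatment has the higher UMEC and/or FF dose.

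**Step 2: what one participant changes.** Planned arm size is 375 (Protocol 9.2.1). The randomized counts in SAP 5.4 give 766 + 643 + 399 + 631 = 2439, and 2439/6 = 406.5 on average.

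- A moved participant who had the event: 1/375 = 0.27 points, or 1/406.5 = 0.25 points, of that arm's incidence.
- A moved participant without the event, or one who was undosed, alters only the denominator. At an illustrative 1% incidence, dropping one of 406 changes it by 1% × (406/405 − 1) = 0.0025 points, about 100 times less.

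**Step 3: how many.** The documents give no count. If 0.1% to 1% of an arm were mainly on the wrong treatment (an assumption), that is 375 × 0.001 = 0.4 to 375 × 0.01 = 3.8 participants per arm.

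**Step 4: why rare events are the exception.** As an illustration, suppose everyone in an arm of 406.5 were treated for 24 weeks or for 52 weeks. Exposure is then 406.5 × 24/52 = 188 to 406.5 person-years. At 8.5 per 1000, that gives 1.6 to 3.5 expected pneumonias. Moving one case is 1/3.5 = 29% to 1/1.6 = 63% of the expected count.

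**The case against.** The strongest reply is that a reader might infer from the randomized-arm rule that every adverse event on a wrong inhaler is charged to a dose the participant did not mainly take. The documents do not support that. Under Section 11.6.1 one wrong container in a fully dosed participant leaves actual equal to randomized treatment. The event is then counted under the dose mainly taken, and tabulating by actual treatment would not move it. This stands.

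Safeguards also exist. Wrong containers are important protocol deviations, with contents identified before database freeze (SAP 11.1) and summarized in Table 1.9. Listings 4, 6 and 21 show randomized against actual treatment, misallocations, and adverse events in participants given an incorrect treatment. This stands as to traceability, but listings do not correct an incidence table.

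On undosed participants, the first double-blind dose is taken in the clinic at Visit 3 (Protocol 6.1), so few should be undosed. They add no exposure time to the person-year tables (SAP 8.2 to 8.4) and no on-treatment laboratory, vital-sign or ECG values. This also stands, and it limits the point to percentage tables.

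Finally, ITT for safety is what Protocol 9.3.1 specifies. A reader might take the SAP to depart from the protocol here; it does not. Nor does the SAP say that the tie rule exists only for safety, since actual treatment is also used in the Pop PK dataset.

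**Conclusion.** The point holds in a limited form. Safety tables count a majority-wrong participant, or one with a tie that resolves to the wrong treatment, under the randomized dose. Any undosed ITT participant sits in percentage denominators without being at risk of an on-treatment event.

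The size cannot be established, because neither the misallocated nor the undosed count is given. It is likely small. A shift of about a quarter of a percentage point per participant applies only when the moved participant had the event; otherwise the change is negligible for any event that is not rare to begin with. A material bias across the safety tables is therefore not shown. The practical stake is rare AESI and MACE, where one case can be a large part of an arm's count. The expectation of bias toward no difference assumes that misallocation is unrelated to outcome.

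This is a cheap improvement to an analysis choice, not an error that threatens the safety conclusions.

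**What to change.** Pre-specify exposure, AE, SAE, AESI and MACE tables in participants who took at least one dose of double-blind treatment, grouped by the actual treatment already derived in SAP Section 11.6.1. At minimum, make them conditional: produce them if any participant's actual and randomized treatments differ, or if any ITT participant was undosed. If neither occurs, nothing changes. Fixing the trigger before unblinding avoids a later choice about whether to show them.

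Record the addition in SAP Section 2.1 as a change from Protocol Section 9.3.1. Keep ITT by randomized arm for efficacy. Events on a wrong inhaler in participants mainly on their planned treatment will stay where they are, and Listing 21 remains the place to identify them.

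The cost is SAP wording, a population and treatment flag in the safety programs, and a few extra tables. Safety denominators may differ slightly from efficacy denominators.
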